8.2 Recording of Adverse Events

At each contact with the subject, study staff must seek information on adverse events by specific questioning and, as appropriate, by examination. Information on all adverse events should be recorded immediately in the source document, and also in the appropriate adverse event module of the case report form (CRF). All clearly related signs, symptoms, and abnormal diagnostic procedures results should be recorded in the source document, though should be grouped under one diagnosis.

All adverse events occurring during the study period must be recorded. The clinical course of each event should be followed until resolution, stabilization, or until it has been determined that the study treatment or participation is not the cause. Serious adverse events that are still ongoing at the end of the study period must be followed up to determine the final outcome. Any serious adverse event that occurs after the study period and is considered to be possibly related to the study treatment or study participation should be recorded and reported immediately.

CONFIDENTIAL

8.3 Reporting of Serious Adverse Events and Unanticipated Problems

Investigators and the protocol sponsor must conform to the adverse event reporting timelines, formats and requirements of the various entities to which they are responsible, but at a minimum those events that must be reported are those that are:

- related to study participation,
- unexpected, and
- serious or involve risks to subjects or others
(see definitions, section 8.1).

If the report is supplied as a narrative, the minimum necessary information to be provided at the time of the initial report includes:

- Study identifier
- Study center
- Subject number
- Current status
- Whether study treatment was discontinued
- The reason the event is classified as serious
- A description of the event
- Date of onset
- Investigator assessment of the association between the event and study treatment

8.3.1 Data and Safety Monitoring Plan (DSMP)

The DSMP is intended to ensure the safety of research participants and the integrity of the study data. [name], M.D., the principal investigator of this study, or one of the other study physicians, will be charged with determining the severity rating of all adverse events. The study staff (P.I., co-investigators, clinical research coordinator) is responsible for collecting and recording all clinical data. As these results are collected, all toxicities and adverse events will be identified, graded for severity and assigned causality, reported to the required entities, and compiled for periodic review. After assigning causality, the P.I. will decide the course of action for the study participant. The P.I. will evaluate every adverse event and determine whether it affects the risk/benefit ratio of the study and whether modifications to the protocol or informed consent form are required. The principal investigator (and, in his absence, physician co-investigators) will differentiate serious from non-serious adverse events. Serious adverse events will be reported to the Penn IRB and the NIAAA project officer within 48 hours and an annual report summarizing all adverse events will be prepared and reported to the UPenn IRB, CMCVAMC IRB, and NIAAA. The following information will be considered in the periodic safety report to the Data and Safety Monitoring Board (DSMB), which will be empanelled prior to initiation of the trial:

- Summary of adverse events.
- Dropout rates and reasons for the dropouts.
- Number of patients who have completed the study.
- Any other relevant information

The DSMB, a full description of which is provided below, will follow guidelines established for monitoring clinical trials in the Center for Studies of Addiction. It should be noted that, at no time will a DSMB member participate in the review of a study in which he or she is a co-investigator or otherwise actively involved.

Any patients thought to be at risk from drinking or psychiatric or medical disorders during treatment will be referred to appropriate clinical services. Given the anticipated moderate effect sizes, we will not conduct interim analyses, nor have we elaborated stopping rules for

CONFIDENTIAL

the study in relation to efficacy. An adequate evaluation of efficacy will require a sample size larger than what will be available before the study is completed as designed. However, if it has been determined, for any reason, that the study should be suspended, we will discontinue enrollment of new patients, while continuing the treatment and monitoring of patients already enrolled in the study, unless to do so would create a risk that is not justified by any potential benefit to patients.

Women of Reproductive Age: As noted above, precautions for pregnant or reproductive age women are in accordance with NIAAA requirements and this will be monitored as part of the DSMP. Women who are pregnant, nursing or of reproductive age and not using effective methods of birth control will be excluded from the study. The study inclusion and exclusion criteria, in total and as specified in the protocol, will be the basis for determining study eligibility. As mentioned above, it is possible that some hormonal contraceptives (e.g., birth control pills, hormonal implants or hormonal injections) may be made less effective by topiramate. If appropriate, the study doctor will discuss with patients alternatives or additional non-hormonal methods of birth control to be used during participation in the study.

Data and Record Safety/Confidentiality: Records, filed in the IRB office, verify that all research project personnel have completed training in the protection of human research subjects in accordance with the guidelines of the U.S. Department of Health and Human Services (DHHS) and the Office for Human Research Protection (OHRP). The study staff (PI, clinical research coordinator, etc.) will keep all study medical records (including any codes to de-identified data) under lock and key in a secure location, as required by law. All electronic data and files (e.g., database, spreadsheet, etc.) containing identifiable patient information shall be password protected. Any computer hosting such files shall have a BIOS password to prevent access by unauthorized users. If patient data are to be exchanged with others, the data will be coded. If identification is necessary, then the data will be encrypted while en-route to the recipient with strong encryption levels (≥ 128 bits for symmetric encryption (DES) and ≥ 1024 bits for asymmetric encryption (RSA)).

All data and blood specimens will be stored without direct identifiable information, but will be identifiable via a linking code. Blood will not be used for the purpose of establishing cell lines. Any hard copy records associated with the study will be kept in locked offices at the clinical site. The secured research records are labeled with code numbers only (names and other identifying information are kept separate from research records). Access to hard copy data is only given to staff members working on the study. Only staff members designated to handle or analyze study samples will have access to the samples and their storage. Coded blood samples are stored in clinic-specific refrigerators and freezers, which are located in secure rooms. As per routine in the Treatment Research Center, all electronic files (e.g., database, spreadsheet) will be password protected. Any computer hosting such files will have a BIOS password to prevent access by un-authorized users.

Data used for safety monitoring will include serious adverse events, dropout rates and reasons for dropout, enrollment numbers, patient interviews, medication compliance, review of symptoms or performance status, review of clinical/diagnostic test results, review of physical examination, review of vital signs, review of evaluation performed, protocol deviations, and blinded data. If it has been determined, for any reason, that there will be a suspension of this study, the PI will suspend enrollment of new patients but continue intervention/monitoring of previously enrolled patients if it is in the best interest of those patients. We have determined that this study involves more than minimal risk to patients, but that potential benefits outweigh potential risks of treatment.

CONFIDENTIAL

Blood will be collected for DNA analysis. The information derived from analysis of the patients' DNA will not be provided to the patient, since at the present time the existing preliminary genetic data to predict the response to topiramate treatment do not provide a basis for genetic counseling. Should that situation change over the course of the treatment trial, procedures will be developed in conjunction with the Penn IRB to provide patients with relevant information on genotype and to counsel them in relation to that information. While the study is open, DNA samples will be coded with a number that provides an indirect link to the patient's identity (samples will be accessible only by the researchers and staff involved with this study). Upon completion of the study the sample will be kept in storage indefinitely. However, the sample will forever be separated from all identifiers. These de-identified samples may be shared with other researchers and used in other projects. The lab procedures for storage include a passcode-protected locked room, and secure storage freezers. All samples will be retained securely as per lab protocols.

8.3.2 University of Pennsylvania School of Medicine, Center for Studies of Addiction, Data and Safety Monitoring Board

Introduction: The Center for the Studies of Addiction, here after referred to as the Center, has identified the need to assist investigators with meeting their ethical responsibility for ongoing study monitoring of treatment outcomes and safety monitoring. Furthermore, NIH Guidelines (1998) specify that all clinical trials should have a system in place for appropriate oversight and monitoring to ensure the safety of participants and the validity of the data. In order to help meet these needs the Center is establishing a committee called a Data and Safety Monitoring Board (DSMB).

Purpose: The purpose of the DSMB is to assure that the safety of study subjects is protected while the scientific goals of the ongoing studies are being met. Specifically, the DSMB is charged with monitoring the safety of participants and the quality of the data, as well as the appropriate termination of studies either when significant benefits or risks have been uncovered or when it appears that a clinical trial cannot be concluded successfully.

Objectives:

- A. To determine which studies conducted at the Center require a Data and Safety Monitoring Board.
- B. To review initial protocols for studies to ensure the following (see Appendix 1):
 - Each protocol captures the information necessary to evaluate the safety and efficacy of the study when it is ongoing and completed and to provide recommendations that may improve the protocol.
 - Each protocol includes a detailed Data Safety and Monitoring Plan (DSMP). This plan, in turn, also references this DSMB plan as well as specifying modifications to the Board plan that are necessary. The DSMP should also include stopping rules that specify the outcome differences detected between groups during an interim analysis that can stop a clinical trial. In general, stopping rules will reflect one of the following conditions:
 1. There is clear evidence of harm or harmful side-effects of the treatment;
 2. There is no likelihood of demonstrating treatment benefit;
 3. There is overwhelming evidence of the benefit of the treatment.
- C. To monitor ongoing protocols to evaluate the following (see Appendix 2):
 - The safety of the subjects as pre-specified in the DSMP of each protocol and independently the DSMB will make recommendations to researchers to continue, to

CONFIDENTIAL

amend, or to terminate a clinical trial based on the interim analysis of the safety data (e.g., terminate a clinical trial because of high incidence of an SAE).

- The efficacy of the treatments being tested as pre-specified in the interim monitoring plan of each protocol and independently make recommendations to researchers to continue, to amend or to terminate a clinical trial based on the interim analysis for efficacy (e.g., terminate a clinical trial because the analyses indicate the study is having a negative effect, the intervention is not adequately implemented or there is no evidence of a treatment effect after the prescribed level of power is reached).
- The presence of early unanticipated therapeutic results, side effects or adverse consequences for each protocol, and independently make recommendations to continue, to amend or to terminate a clinical trial based on the interim analysis for efficacy (e.g., terminate a clinical trial because it would be unethical to continue the non-treatment compared to the treatment-as-usual arm).
- The performance of each trial (e.g., protocol violations, improper entry criteria, slow accrual rate, low participation rate, failure of randomization, inadequate treatment adherence, inadequate follow-up rate, severely compromised validity), and to independently make recommendations for improvement or termination if the trial would be unable to prove anything meaningful, regardless of modifications.

8.3.3. Studies Requiring a DSMP and DSMB

All clinical trials involving human subjects require study-specific IRB approval and a detailed DSMP, and will be reviewed by the Center's DSMB. The DSMB will make a determination regarding studies that require ongoing DSMB review. The National Institutes of Health policy on data and safety monitoring will serve as a guide to the DSMB in making decisions regarding trials that require DSMB oversight and monitoring. As such, all phase III clinical trials are required to have data safety and monitoring in the form of a DSMB. Phase I or II trials will be required to have DSMB oversight for the following reasons: if the investigator is the investigational new drug (IND) holder, if the study has multiple clinical sites, is blinded, or employs a particularly high-risk intervention or vulnerable population. Additionally, a DSMB may be indicated when there are special concerns regarding subject safety, a study investigator is inexperienced or where study integrity could be enhanced by the independence of the DSMB. The DSMB's role is oversight above and beyond that of the Institutional Review Board. The intent of the board is not to place an onerous burden on investigators. If a trial has the oversight of an external DSMB there does not need to be duplication of effort.

8.3.4. Scope of Data Monitoring

The precise nature of the data to be monitored and the analyses used per protocol will be determined by the DSMB. The primary source of the data will be the Case Report Form developed for each protocol. The study investigators, as requested by the DSMB, will provide additional detailed information regarding serious adverse events.

A. Study Admission Data: The DSMB will assess the sites' performance with respect to subject recruitment. Monitoring of admission data will include the number of subjects calling for treatment for substance use/abuse problems, number of subjects scheduled for an intake appointment, number of subjects who attended an intake appointment, and number of subjects admitted to the study. The DSMB may request a report of the reason why subjects were disqualified from participating in the study. For subjects admitted to the study, the

CONFIDENTIAL

DSMB will review eligibility criteria for admitted subjects, any protocol violations, and the demographic distribution of the subjects (by group if required) (see Appendix 2).

B. Protocol Compliance: The DSMB will monitor the data per protocol to assess compliance with the protocol including adherence to protocol participation rules for safety or administrative adherence. Examples of participation rules might include, for example, stopping participation or withholding treatment for elevations of liver function tests, severe neuropsychiatric disturbances or changes in vital signs. The DSMB will also monitor the quality and completeness of the data being collected. For data collected at specified times the Board should monitor the frequency of missing or erroneous data, and presence and frequency of outliers.

C. Safety Data: Monitoring of safety data will include per protocol a review of Adverse Events (AE's) and Serious Adverse Events (SAE's), and data commonly accepted to reflect differences in safety between treatment groups such as clinical laboratory data, treatment retention, and reason for drop out. Safety information for all studies will be reported to the Board in a blinded manner. The Board may determine if a review of unblinded data is indicated. Unblinded information will only be discussed during closed meeting sessions. Furthermore, the Board may request formal statistical analyses of the safety data.

For non-serious AE's, data may be summarized by treatment groups, with data on individual subjects available for DSMB review as needed and if the study blind is not compromised. For SAE's, data will include all of the adverse event data that meet the FDA definition of serious adverse events. In the assessment of SAE's, the DSMB will review each individual case including treatment group assignment.

After each meeting of the DSMB, the executive secretary will forward a summary report of all serious and unexpected adverse experiences to each investigator per protocol. The report will document that a review of data and outcomes took place on the date of the meeting. It will summarize the Board's review of cumulative serious and unexpected adverse events reported without specific disclosure by treatment arm. Furthermore, the report will inform investigators of the Board's recommendations with respect to progress or need for modification of the protocol. The principal investigator is required to transmit the report to the local IRBs.

The DSMB will follow up on the outcome of AE's and SAE's, and that all appropriate AE's and/or SAE's are reported to the UPenn IRB, CMCVAMC IRB, FDA, NIH or other pertinent regulatory agency.

D. Efficacy Data: Efficacy data determined by the protocol are based on the primary and secondary outcome variables detailed in the DSMP for each component which will be required to have been reviewed and accepted by the DSMB. The data may be presented for all treatment groups combined or by treatment groups. Data by treatment groups can be presented to the DSMB blinded and then the DSMB may request to unblind the data. In the event that a safety concern arises that requires an interim analysis of efficacy data, an analysis may be made on a for-cause basis. Any for-cause interim analysis requested by the DSMB should specify in advance the efficacy outcome of interest, the number of comparisons to be made for purposes of the analysis, the statistical method to be employed in the analysis, the significance required to reach a decision, and the new p value necessary to reject the null hypothesis should the study run to completion (such that the probability of a Type 1 error is maintained at <0.05 for all primary analyses that would be conducted).

CONFIDENTIAL

For studies that are conducted in a blinded manner, the presentation of data relating specifically to outcome measures should be presented to the DSMB in the manner and timing described in the DSMP for that study. Additionally, the Board will determine whether interim analyses of efficacy data are required. Studies that include interim analysis of efficacy data should provide the proposed number of interim analyses to be made, the specific comparisons to be made at each such analysis, the stopping rules on the basis of efficacy findings, including both standards for the determination of 'overwhelming efficacy' and an 'inevitable failed trial', and the methods of statistical correction to be used to control the final overall Type 1 error. When defining this interim review in the protocol, consideration should be given to whether the data can be prepared for the DSMB review in a sufficiently timely manner so that any resulting decision can in fact impact on the study if the study is largely completed before the conclusions are made, the interim review may be unnecessary.

E. Establishing a DSMB

- Board membership: The DSMB will consist of at least four members. Three members will constitute a quorum. The Center's Executive Committee will approve the composition of the DSMB, and appoint the members. The term of membership for the DSMB will be for three years.
 - The DSMB members will include [name]. (Chair), [name]., [name]., [name], MSN, CRNP, ANP-BC, [name]., [name]., [name]., CRNP, [name]. (biostatistician) and [name]. (alternate biostatistician).
 - Because board members should be free of financial interest that could be substantially affected by the outcome of the trial, conflict of interest disclosure documentation is necessary to avoid real or apparent conflict of interest of the DSMB members. Individuals invited to serve on the DSMB should disclose in writing to the sponsor any potential conflicts of interest, actual or implied by appearance. Should an unanticipated situation arise that the Board member feels represents a conflict of interest, the Board member should recuse themselves from deliberations. At the start of each new member's term, the individual will sign a confidentiality statement promising not to disclose any proprietary and nonproprietary data. Furthermore, no disclosure should be made of the deliberations of the Board.
 - The DSMB may identify the need for inclusion of scientists or non-scientists that may provide unique insights to a particular study or aspect of a study. These individuals could be a clinical pharmacologist, a medical ethicist or an individual that could bring the perspectives of the population under study. Whenever a project is reviewed that directly involves one of the board members, alternate members will be chosen to review the study or studies in question. At no time will a board member be involved in the review of his or her own study.

F. Board meeting schedule: The DSMB meetings will be held annually. The Board has the option of expedited meetings to review unexpected SAEs or other urgent issues that may arise during the course of the trials. Unscheduled meetings may be recommended and initiated by the Chair of the DSMB or the sponsor (or the principal investigator) of the study. The data and any other relevant materials to be reviewed by the DSMB will be made available to the Board members at least two weeks before the meeting. Investigators will be informed that their protocol is scheduled for on-going review by the DSMB at least two months before

CONFIDENTIAL

the meeting. Should an investigator wish to have a non-emergent item placed on the agenda of an upcoming DSMB meeting, the investigator should place their request in writing to the Chair of the DSMB. The investigator will be notified of the outcome regarding their request at least two weeks before the scheduled meeting.

G. Conduct of the Meetings: The DSMB meetings will be divided into three sessions: open, closed and executive. The Principal Investigator and other study staff per protocol will attend the open session and will present relevant information to the Board about general aspects of the trial. The open session may focus on the background of the study, the protocol, status of the study, problems with accrual and follow-up, baseline demographic data, compliance issues, frequency of adverse events, documentation of endpoints, data quality issues, flow of forms, data based protocol modification issues, and any other issue regarding the studies under review that can be discussed without reference to interim comparative results.

Following the open session, a closed session will be held. During the closed session, the DSMB chair or representative will conduct the review of all issues and put each issue to a vote. A quorum for the DSMB is (4) voting members. This session will be attended by the DSMB members, the DSMB executive secretary, and if necessary the principal investigator. During the closed session, the discussions will focus on the treatment safety, efficacy data, whether the primary study question has been answered, the interim results by treatment arm (usually masked), determining when study data may be released and reviewing requests for access to the results of the interim analysis, and updating the Board on actions taken related to their actions and recommendations of the previous meeting.

Following the closed session, an executive meeting may be held. The executive meeting is restricted to DSMB members (voting and non-voting members). During these sessions, the Board may discuss any unmasked analysis of a blind clinical trial and any sensitive issues surrounding the clinical trials under review.

H. Report Format: Reports to the DSMB may include reports from the Data Management Center that reflects the status of the study, progress or findings to date, and any relevant issues. Additionally, data are presented that describe the administrative status of the study including recruitment. Reports should also provide a safety assessment and may include copies of monitoring reports. Recommendations related to clinical trials will be made in writing by the Board's Chairperson to the principal investigator of the trial. Normally, results of the interim analysis will not be disseminated. Only under certain conditions should the results be released. The Board should make the final decision related to the release of this information.

The Board Chairperson will prepare the draft report of the meeting, with the assistance of the Executive Secretary. The Executive Secretary will be responsible for the preparation of meeting minutes for inclusion in the DSMB report. The report will outline and summarize all discussions during the open and closed sessions of the meeting. Recommendations and action items will be clearly marked within the body of the report. If the DSMB decides to conduct an executive session, a statement will be included in the Minutes of the Meeting stating an executive session was conducted, but should not disclose the contents of the discussions. Minutes for the executive session will be recorded separately and not distributed beyond the DSMB members. The draft report will be reviewed and edited by all Board members prior to issuance of the final report. The Principal Investigators will ensure that their reports are sent to the UPenn IRB, CMCVAMC IRB, NIH or others, as indicated.

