5.8 Blinding of Study Drug

All subjects and research staff will be blinded as to whether the subject is in the topiramate or placebo group until the decision to break the study blind is determined at the end of the study (after study database lock). Codes linking randomization number for each subject to actual treatment will be secured in a sealed, opaque envelope and maintained in a locked drawer in the research pharmacy and the hospital pharmacy. Research subjects will be given the emergency contact number for the study during the consenting process. See section 8.4 (Unblinding Procedures) for a description of the process for unblinding a study subject.

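### The DSMB section allows the principal investigator into the closed session, where by-arm or unblinded data may be discussed, and no rule requires the investigator to leave

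*Combined protocol and SAP*

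**What the plan says.** **Attendance.** Section 8.3.4 G divides board meetings into open, closed and executive sessions. Of the closed session it says: "This session will be attended by the DSMB members, the DSMB executive secretary, and if necessary the principal investigator".

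**Closed-session content.** Item G lists treatment safety, efficacy data and "the interim results by treatment arm (usually masked"). Item C of the same section says: "Unblinded information will only be discussed during closed meeting sessions". Item C also says: "In the assessment of SAE's, the DSMB will review each individual case including treatment group assignment". It does not say in which session that review takes place.

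**Executive session.** Item G restricts it to board members. It may be held after the closed session, and the board may discuss unmasked analyses there.

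**Blinding.** Section 5.8 says: "All subjects and research staff will be blinded as to whether the subject is in the topiramate or placebo group", and this lasts "until the decision to break the study blind is determined at the end of the study (after study database lock").

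**The investigator's role.** Section 8.3.1 (DSMP) says: "The study staff (P.I., co-investigators, clinical research coordinator) is responsible for collecting and recording all clinical data". The investigator or another study physician "will be charged with determining the severity rating of all adverse events". The investigator also evaluates every adverse event, chooses the participant's course of action after assigning causality, and determines whether the protocol or consent form needs modification.

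**The concern.** The closed session is where the plan places unblinded information, yet the plan admits to it someone who is meant to stay blinded. The condition on attendance is whether the investigator is needed. It is not whether the material on the table is masked.

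What is at stake is the independence of safety judgements. The safety comparisons in section 3.4 include the frequency of severe events and of events rated moderate or severe, so they depend on severity ratings that the investigator may make. An investigator who has seen which arm serious events fell in could, without intending to, rate later events, attribute cause or judge the need for protocol changes differently.

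**Working it through.** No arithmetic applies, because the point depends on no sample size, error rate or effect size. The check is to set the provisions side by side.

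1. **Is the investigator covered by the blinding rule?** Section 5.8 covers research staff. Section 8.3.1 lists the investigator among study staff and as one of the study physicians. Section 6.8 keeps study physicians blinded even after the six-month visit, when subjects may learn their own assignment. I read the rule as covering the investigator.

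2. **What may be shown in the closed session?** Item C makes closed sessions the only place for unblinded information. Item G adds interim results by arm, masked usually but not always.

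3. **Which material would breach section 5.8 directly?** That section protects the assignment of the individual subject. The serious adverse event review in item C pairs each case with its treatment group, which is exactly subject-level information. Because no session is named for it, it could take place with the investigator present.

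4. **Does the executive session close the gap?** Only in part. Both the session and the discussion of unmasked analyses in it are optional, and no sentence says such material may be discussed only there. Item C names closed sessions instead. If item C means any non-open session, the two items agree, but the text does not say so.

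5. **Is there a recusal rule?** None requires the investigator to leave the closed session when by-arm or unblinded material comes up.

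6. **Is there another route?** Item H has the meeting report summarise closed-session as well as open-session discussion, and withholds only executive-session content. Investigators are to forward their reports to the IRBs and others, so they evidently receive them. Item C limits this for the summary of serious and unexpected events, which must not disclose results by arm. No equivalent limit is stated for the rest of the closed-session summary.

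7. **Does the attendance clause fit the rest of the section?** It does not. Item G keeps the open session, which the investigator attends, free of interim comparative results, and item H says interim results are normally not disseminated.

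**The case against.** The strongest case on the other side has five parts.

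- **Both rules can be followed.** Attendance is conditional. Item C has safety information go to the board blinded by default, and item D lets by-group efficacy data be presented blinded first. If the investigator attends only for masked items, section 5.8 is respected. This stands. A reader might infer that the attendance rule and the blinding rule cannot both hold, but the documents do not support that. They support only that a breach is permitted.
- **There is a members-only session for unmasked analyses.** This is a real safeguard, but it is optional and not exclusive.
- **Efficacy exposure is largely hypothetical.** Section 8.3.1 plans no interim analyses, and its list for the periodic report covers adverse events, dropouts, completers and other relevant information. This stands. By-arm efficacy would arise only if the board asked for it, which item D allows. A reader might count annual meetings over a five-year study as several exposures. Nothing shows that the investigator would be called in, or that unmasked data would then be on the table.
- **The investigator is not the sole grader.** Another study physician may rate severity, so the inference that the investigator grades every event is too strong. The duty to evaluate every event remains. A reader might also infer bias in self-reported drinking through the staff involved, but the documents give no basis for it.
- **Masked tables do not unblind subjects.** Section 1.5 gives numbness and tingling as 49% against 6%, so a reader might infer that arm-coded tables amount to unblinding. They might reveal which code is topiramate, but not by themselves any subject's assignment, which is what section 5.8 protects.

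It is also fair to say that this is the Center's general board text. It is nevertheless part of this protocol, and section 8.3.1 applies the board to this trial.

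**Conclusion.** The concern holds as a gap in the protection of the blind. Followed as written, the text lets a blinded investigator with responsibility for every adverse event sit in a session where by-arm or unblinded material may be discussed. It does not make unblinding certain or show that it would be frequent.

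The size of any effect cannot be derived from the documents. The most plausible route is by-arm safety data, above all serious adverse events reviewed with treatment assignment. The conclusion rests on two readings: that the investigator is among the staff blinded under section 5.8, and that closed sessions in item C include the closed session described in item G. The change is worth making because it is cheap and protects safety judgements.

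**What to change.** Either of two changes closes the gap:

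- **Preferred:** remove the principal investigator from closed-session attendance, and route board questions in writing or through a reconvened open session without by-arm data.
- **Alternative:** keep the attendance clause, but confine all by-arm and unblinded material, including serious adverse event review with treatment assignment, to the members-only executive session.

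The natural place is a study-specific modification in this trial's monitoring plan, which section 8.3.2, objective B, provides for. The Center's general text then need not change. Section 8.3.4 G could be edited instead.

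With either change, reconcile items C and G on where unblinded material is discussed, name the session for serious adverse event review, and keep by-arm content out of the closed-session summary in the item H report.

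The cost is a few sentences. Under the preferred option the board also loses the convenience of questioning the investigator during closed discussion. No analysis, sample size or data collection changes.
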